Intervention goals	1. improving the risk awareness of inactive lifestyle and unhealthy diet 2. stimulating positive outcome expectancies and motivating intention formation	1. enhancing motivational self-efficacy for PA and FVI 2. setting a general goal of health behavior and forming the intention of PA and FVI	1. setting action plans for PA and FVI 2. boosting motivational self-efficacy for PA and FVI	1. further confirming appropriate action plans for PA and FVI 2. further enhancing motivational self-efficacy for PA and FVI	1. setting coping plans for PA and FVI 2. enhancing self-efficacy on maintaining PA and FVI	1. further confirming appropriate coping plans for PA and FVI 2. further enhancing self-efficacy on maintenance of PA and FVI	1. promoting perceived social support on PA and FVI 2. enhancing recovery self-efficacy to prevent unhealthy behaviour relapse	1. further promoting perceived social support on PA and FVI 2. further enhancing recovery self-efficacy to prevent unhealthy behaviour relapse
Intervention Content	informing the risk of inactive behaviour and unhealthy diet introducing and promoting the benefits of physical activity (PA) and fruit and vegetable intake (FVI).	assessing motivational self-efficacy; encouraging patient to build confidence in PA and FVI setting goals for PA and FVI, as well as general health goal	learning how to make specific action plans for PA and FVI taking examples of successful case about action plan implementation	reviewing the implementation of action plans; adjusting action plans taking examples of successful case about action plan implementation and adjustment	finding difficulties of plan implementation, making coping plan taking examples of successful case about health behaviour adherence	reviewing the implementation of coping plans; adjusting coping plan Take examples of successful case about health behaviour adherence	reviewing perceived social report on PA and FVI taking examples of successful case about behaviour relapse prevention	further reviewing perceived social report taking examples of successful case about behaviour relapse prevention

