Additionally, some behaviour change techniques will be employed in the intervention in order to facilitate the implementation and maintenance of behaviour. For example, two types of feedback will be provided. Participants will receive individualized feedback on their behaviour performance 4 weeks ago, 3 weeks ago, 2 weeks ago and 1 week ago respectively. In addition, normative feedback on the criterion-based behaviour recommendation will be presented as well (e.g., accumulated at least 150 minutes with moderate intensity of PA per week, 5 portions of FVC per day) (see example in Figure 2). Moreover, examples of role models will be provided throughout the intervention to support participants to set goals and develop plans.

In addition to the intervention on web-site, SMS reminder will be sent to participants weekly prior to each intervention program in order to remind patients to attend the weekly intervention (e.g., "Dear patients, the coming learning session will start tomorrow. We kindly remind you to participate in it by clicking the hyperlink showed on the Wechat tomorrow. Have a nice day! "). Sequentially, Wechat message will be sent to participants on the next day for accessing the intervention website (e.g., "Here is the intervention hyperlink for Week two. Please click on it. www.ehealthlearningchina.com/patient/two_b.php").

[figure not shown]

Figure 2: Individualized and normative feedbacks regarding the portion of fruit and vegetable intake in average per day

Measures:

The standardized electronic questionnaires have been validated in the previous pilot study with Chinese cardiac patients (Liang, Duan et al., 2017), which consists of the following four parts.

1. Behaviour indicators

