Physical activity (PA): The level of PA will be measured through the short Chinese version of the IPAQ questionnaire (Macfarlane et al., 2007). Participants will be asked to estimate the number of days and hours spent for vigorous, moderate and walking activities during the past week. **Fruit and vegetable intake (FVI):** FVI will be measured with four items, including fruit or vegetable juice, fruit, cooked or steamed vegetables, and raw vegetables (Rafferty et al., 2002). Respondents will be asked to count the number of portions of fruit and vegetables they consumed on average during a typical day. **Combined healthy lifestyle indicator:** In order to combine two behaviours, PA and FVI will be categorized according to whether or not the participants meet the health recommendations ([name], Fleig, Wiedemann, & Schwarzer, 2015). Based on the health guidelines for cardiac patients, the thresholds of 150 minutes PA per week (WHO, 2010) and 5 portions of fruit and vegetables (WHO, 2004) will be chosen. We use 1 and 0 to denote whether participants meet both recommendations or not.

2. Social-cognitive indicators of PA and FVI

Self-efficacy: Self-efficacy will be assessed with three dimensions consisting of motivational, maintenance and recovery self-efficacies with the stem "I am certain that..." followed by 5 items for PA such as "...I can be physically active permanently at a minimum of 5 days a week for 30 minutes even if it is difficult", or followed by 5 items for FVI such as "...I can eat 5 portions of fruit and vegetable a day even if it is difficult." (Cronbach's α for PA= .88; Cronbach's α for FVI= .92) (Luszczynska & Sutton, 2006). **Intention:** Intention for PA will be assessed with the stem "I intent to do for at least 30 minutes as day on minimum 5 days a week or at least 150 minutes a week with..." followed by 3 items such as "... vigorous sport", "...moderate PA" and "...mild PA". Intention for FVI will be measured by the stem "I seriously intend to..." followed by 3 items such as "eat at least 5 servings of fruit and vegetable each day"

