1. Physical activity behaviour

We are interested in finding out about the kinds of physical activities that people do as part of their everyday lives. The questions will ask you about the time you spent being physically active in the last 7 days. Please answer each question even if you do not consider yourself to be an active person. Please think about the activities you do at campus, such as, to get from place to place, and in your spare time for recreation, exercise or sport.

Think about all the vigorous activities that you did in the last 7 days. Vigorous physical activities refer to activities that take hard physical effort and make you breathe much harder than normal. Think only about those physical activities that you did for at least 10 minutes at a time.

(1). During the last 7 days, on how many days did you do vigorous physical activities like heavy lifting, digging, aerobics, or fast bicycling?

_____ days

No vigorous physical activities

(2). How much time did you usually spend doing vigorous physical activities on one of those days?

_____ hours per day

_____ minutes per day

Think about all the moderate activities that you did in the last 7 days. Moderate activities refer to activities that take moderate physical effort and make you breathe somewhat harder than normal. Think only about those physical activities that you did for at least 10 minutes at a time.

(1). During the last 7 days, on how many days did you do moderate physical activities like carrying light loads, bicycling at a regular pace, or doubles tennis? Do not include walking.

_____ days

No moderate physical activities

(2). How much time did you usually spend doing moderate physical activities on one of those days?

_____ hours per day

_____ minutes per day

Think about the time you spent walking in the last 7 days. This includes at work and at home, walking to travel from place to place, and any other walking that you have done solely for recreation, sport, exercise, or leisure.

(1). During the last 7 days, on how many days did you walk for at least 10 minutes at a time?

_____ days

No walking

(2). How much time did you usually spend walking on one of those days?

_____ hours per day

_____ minutes per day

Which intentions do you have for the near future?

I intent to do for at least 20 minutes a day on minimum 2 days a week (or at least 40 minutes a week)...

		not true			exactly true

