1.	... perform strenuous physical activity (heart beats faster, sweating)	 ₁	 ₂	 ₃	 ₄
2.	... be moderately physically active (not fatiguing, mild sweating)	 ₁	 ₂	 ₃	 ₄
3.	... be mildly physically active (hardly strenuous, no sweating)	 ₁	 ₂	 ₃	 ₄

3. Plans of physical activity

For the next month I already planned in detail ...

		Totally disagree			Totally agree	
1.	... which concrete physical activity I will pursue (e.g. walking).	 ₁	 ₂	 ₃	 ₄	 ₅
2.	... where I will be physically active (e.g. in the park).	 ₁	 ₂	 ₃	 ₄	 ₅
3.	... on which days I will be physically active (e.g. every Tuesday and Friday).	 ₁	 ₂	 ₃	 ₄	 ₅
4.	... when I have to be especially cautious not to stop being active.	 ₁	 ₂	 ₃	 ₄	 ₅
5.	... what I can do in difficult situations, in order to remain true to my own resolutions	 ₁	 ₂	 ₃	 ₄	 ₅
6.	...how I can stay active, even if something happened	 ₁	 ₂	 ₃	 ₄	 ₅

4. Perceived Social Support of physical activity

		not true			exactly true
1.	My partner supports me to stay physically active	 ₁	 ₂	 ₃	 ₄
2.	People from my family supports me to stay physically active	 ₁	 ₂	 ₃	 ₄
3.	People like my friends helps me to stay physically active	 ₁	 ₂	 ₃	 ₄

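### The printed questionnaire asks about intending 40 minutes of physical activity a week, while Measures defines the same intention scale at 150 minutes a week

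*Combined protocol and SAP*

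**What the plan says.** All references are to the combined protocol and SAP.

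- **Section 6, Measures, social-cognitive indicators (Intention).** The stem is "I intent to do for at least 30 minutes as day on minimum 5 days a week or at least 150 minutes a week", followed by three items for vigorous, moderate and mild activity.
- **Attached questionnaire, Part I, PA intention items.** The stem is "I intent to do for at least 20 minutes a day on minimum 2 days a week (or at least 40 minutes a week"). The three items, each answered on a 1–4 scale, are "perform strenuous physical activity (heart beats faster, sweating"), "be moderately physically active (not fatiguing, mild sweating") and "be mildly physically active (hardly strenuous, no sweating").
- **Other PA levels in the plan.** The combined lifestyle indicator uses "the thresholds of 150 minutes PA per week". The normative feedback presents "accumulated at least 150 minutes with moderate intensity of PA per week". All three PA self-efficacy stems on the same questionnaire are set at 5 days of 30 minutes.
- **Role of the scale.** Objective 2 names intention among its social-cognitive outcomes. Objective 4 tests the social-cognitive variables as mediators. Table 1 gives as a week 2 goal "setting a general goal of health behavior and forming the intention of PA and FVI".
- **Validation and reliability.** Measures describes the questionnaires as already validated in a pilot with Chinese cardiac patients, and reports a Cronbach's alpha of 0.34 for PA intention.

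**The concern.** The form is what patients answer, so its wording decides what is measured. If it goes out as printed, the report would describe a 150-minute intention while the data refer to a 40-minute one. The mediation model would then relate an intention at one level to a lifestyle outcome at another, beside a self-efficacy mediator set at the outcome's level. With two wordings on file, neither the validation statement nor the alpha of 0.34 can be tied to one stem. Once T1 data have been collected, the baseline wording can no longer be changed.

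**Working it through.** **1. Is it the same scale?** Measures lists vigorous, moderate and mild activity. The form lists strenuous, moderate and mild activity. Both have three items graded by intensity, and no second PA-intention scale appears. It is one scale with two stems.

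**2. Does each stem agree with its own weekly total?** Weekly minutes = minutes per day × days per week.

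- Form: 20 × 2 = 40, as printed.
- Measures: 30 × 5 = 150, as stated.

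Minutes, days and total all differ, and each set is consistent in itself. A single mistyped digit or a PDF reading error is therefore an unlikely explanation.

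**3. Size of the difference, per item.**

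- Ratio: 40/150 = 26.7%. Equivalently, 150/40 = 3.75.
- Gap: 150 − 40 = 110 minutes a week.

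**4. Which levels does the rest of the plan use?**

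| Place | Weekly PA level |
|---|---|
| Measures, intention stem | 150 min |
| Measures, combined lifestyle threshold | 150 min |
| Intervention, normative feedback | 150 min |
| Questionnaire, PA self-efficacy stems | 5 × 30 = 150 min |
| Questionnaire, PA intention stem | 40 min |

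The parallel diet scale follows the same pattern as the first four rows. Its first intention item asks about at least 5 portions a day, which is the diet threshold in the lifestyle indicator. The printed PA-intention stem is the only one of these set below its behavioural threshold.

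**5. What does a top answer imply?** Both stems say *at least*, so a top answer sets a lower bound on the intention and does not estimate it. The document does not say whether the three items are to be read as overlapping or as separate amounts, so both readings are shown as assumptions for a patient who gives the top answer to all three.

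- Printed stem, overlapping: at least 40 minutes (27% of 150).
- Printed stem, separate amounts: at least 3 × 40 = 120 minutes (120/150 = 80%).
- Measures stem, overlapping: at least 150 minutes.
- Measures stem, separate amounts: at least 3 × 150 = 450 minutes.

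Under either reading, the top score on the printed form is compatible with an intention below 150 minutes. It is equally compatible with one of 150 or more.

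**The case against.** Four arguments stand on the other side.

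**A ceiling effect is not shown.** A reader might infer that patients will score at the top at baseline, so that the item misses the rise the intervention aims for. No score distribution is given, and for the strenuous item a ceiling is far from obvious. The account of the investigators' own work reports pilot effects on all psychosocial variables, with η² from .09 to .23, and treats the pilot's measurement tools as the foundation for this study. If the pilot used the 40-minute stem, that stem detected change. If it used the 150-minute stem, the attached form may simply be out of date. The document does not say which. The loss of sensitivity therefore remains plausible but unquantified.

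**The document does not settle which stem is intended.** This is correct. The agreement of the other PA levels makes Measures a reasonable default but does not prove it. Aligning the form also leaves a mismatch: the stem applies 150 minutes to each intensity separately, whereas the feedback attaches 150 minutes to moderate intensity. It would not turn the three-item score into a measure of total intended minutes.

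**Time is already reserved.** The research schedule gives months 1–4 partly to work on the questionnaires, and the grant template calls for a draft questionnaire. This lowers the risk that the discrepancy survives to T1. It does not name the discrepancy or resolve it.

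**The reach is limited.** PA intention is one of several Objective 2 and 4 variables, and Objective 1 does not use it. The reported alpha of 0.34 is a separate weakness of the scale, and changing the stem is not shown to improve it.

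None of this explains why one scale has two definitions.

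**Conclusion.** The contradiction is certain: one scale, two stems, 40 against 150 minutes a week (27%, a gap of 110 minutes per item). If the form is used as printed, an Objective 2 outcome and candidate Objective 4 mediator is not measured as the plan defines it. It also sits below the level used for the lifestyle threshold, the feedback and PA self-efficacy. This should be fixed before data collection.

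Two stronger readings are not supported. One is that top scorers on the printed form intend less than 150 minutes. Because the stem sets a minimum, their answers do not show this. The other is that the comparison between groups is biased. The form is described as the same for both groups and all three time points, and no such bias is claimed. The share of patients affected and the effect on the Objective 2 and 4 results cannot be derived from the document.

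The reference to campus activities in the introduction to the PA behaviour questions does not fit cardiac outpatients. It concerns a different instrument, has no shown effect, and is a side note only.

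**What to change.** Before the first T1 questionnaire is sent:

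1. **Reconcile the two texts and use one wording at T1, T2 and T3.** By default, replace the figures 20, 2 and 40 in the printed stem with the Measures figures 30, 5 and 150, phrased so that the stem reads on to the three items. This matches the PA self-efficacy stems and the lifestyle threshold.
2. **If the pilot validated the 40-minute stem and the team keeps it,** correct the Intention paragraph in Measures instead. State there that PA intention is measured below the 150-minute threshold, so that the mediation results are read accordingly.
3. **In either case, state** which wording the pilot validated and which wording gave the alpha of 0.34.
4. **List this check** within the questionnaire work scheduled for months 1–4.

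The cost is one line in an electronic form or one sentence in Measures, plus a short statement on the pilot. The downside of aligning the form is possible loss of comparability with pilot data. If the 40-minute stem was the validated one, the aligned stem is also untested.

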[name], the Co-I, would be contributing to the validation of intervention materials, data collection, and data analysis. He will also assist on writing of the final report. He is expected to spend an average of 8 hours/week on this project.

A full-time research assistant would assist website set-up and function test, main study implementation, data management and analysis, and report writing. She/he is expected to spend an average of 40 hours/week on this project.

19. International Collaboration (applicable to ARTS/SOSC/COMM/BUS/AVA)

For ARTS/SOSC:

Please provide the following supplementary information below:

(a) outline how cross-cultural/non-local collaboration would enhance the quality of research;

AND

(b) involve collaboration between an eligible Arts/Social Sciences faculty member and a named co-investigator from outside Hong Kong.

For BUS/COMM/AVA:

Please provide the following supplementary information below:

(a) a description and value of the collaboration;

(b) connection to international institutions;

(c) statement of outcome;

(d) scope or potential for future collaboration; and

(e) brief C.V. of international partners.

N/A

20. Research ethics/safety approval:

Please tick '✓' the appropriate box(es) to indicate approval required, if any, from the Committee on the Use of Human and Animal Subjects in Teaching and Research (HASC).

(If "none" is the response, please indicate also.)

Human Research Ethics	
Animal Research Ethics	
Biological Safety	
Ionizing Radiation Safety	
Non-ionizing Radiation Safety	
Chemical Safety	
None	

- * If approval is required, please also submit the HASC application through the RPS via BUniPort (under the same FRG reference no. under "Research Grant & Output" > "My HASC") after filing the FRG application to Graduate School.

**** Please note proposals from ALL Specialist Panels should first seek relevant ethical/safety approval from the HASC before the Panels can make the funding decision.**

21. Curriculum vitae of investigators:

(Please submit a brief CV* for all investigators relevant to the proposed area of research. - **one CV for each separate proposal.**)

* The brief CV should contain the following information only:

- (i) education **background**;
- (ii) employment history;
- (iii) publication list (for the previous 5 years.)
(**Chinese Medicine & Science Panel applicants** - indicate publications or submitted manuscripts arising from your previous or ongoing projects.) and
- (iv) research activities (for the previous 5 years).

**** Please note that an academic must have produced at least one publication/research outputs within the immediate past two years in order to be eligible to apply for FRG projects.**
